11.5 Data Handling and Analysis

Paper CRFs must be completed from source, signed and dated by members of the site research team. CRFs will then be entered directly on to the RATE-AF database by members of the RATE-AF Trial Office. Randomisation of the trial must be completed by an authorised member of the site research team (as delegated on the **RATE-AF** Trial Signature and Delegation Log) within the timeframe listed in **Table 5**. Copies of all completed CRFs should be filed in the site file. Entries on paper CRFs should be made in ballpoint pen, in black ink, and must be legible. Any errors should be crossed out with a single stroke, the correction inserted and the change initialled and dated. If it is not obvious why a change has been made, an explanation should be written next to the change.

CRFs can be entered by CTU staff or viewed online by site staff at <http://www.bctu.bham.ac.uk/RATEAF>. Authorised staff at sites will require an individual secure login username and password to access this online data system.

Data reported on each CRF should be consistent with the source data or the discrepancies should be explained. If information is not known, this must be clearly indicated on the CRF. All missing and ambiguous data will be queried as detailed in the Trial Data Management Plan. All sections are to be completed.

CRF versions may be updated by the **RATE-AF** Trial Office, as appropriate, throughout the duration of the trial. Whilst this will not constitute a protocol amendment, new versions of the CRFs must be implemented by participating sites immediately on receipt.

It will be the responsibility of the Principal Investigator to ensure the accuracy of all data entered in the CRFs. The **RATE-AF** Trial Signature & Delegation Log will identify all those personnel with responsibilities for data collection.

Access to data, including the final trial dataset, will be limited to members of the Research Team.

The investigator(s)/institution(s) will permit trial-related monitoring, audits, REC review, and regulatory inspection(s), providing direct access to source data/documents. Trial participants are informed of this during the informed consent discussion and will consent to provide access to their medical notes.

Table 5: Data Collection Forms

Form Name	Schedule for submission
Randomisation Form	Collected at randomisation
Baseline and Follow-Up CRFs	As soon as possible after each follow-up assessment time point
Serious Adverse Event Form	Faxed within 24hrs of research staff at site becoming aware of event

11.6 End of Trial

The end of trial will be 30 days after the last data capture. This will allow sufficient time for the completion of protocol procedures, data collection and data input. The Trials Office will notify the MHRA and REC that the trial has ended within 90 days of the end of trial. Where the trial has terminated early, the Trials Office will inform the MHRA and REC within 15 days of the end of trial. The Trials Office will provide them with a summary of the clinical trial report within 12 months of the end of trial.

A copy of the end of trial notification as well as the summary report is also sent to the University of Birmingham Research Governance Team at the time of sending these are sent to the MHRA and REC.

11.7 Archiving

Archiving will be authorised by the BCTU on behalf of the Sponsor following submission of the end of trial report.

Principal Investigators are responsible for the secure archiving of essential trial documents (for their site) as per their NHS Trust policy. All essential documents will be archived for a minimum of 25 years after completion of trial.

Destruction of essential documents will require authorisation from the BCTU on behalf of the Sponsor.

12 Statistical Considerations

12.1 Outcome measures

12.1.1 Primary Outcome

Patient-reported quality of life (QoL) - SF-36 physical component summary score at six months

12.1.2 Secondary Outcomes

Patient-reported QoL:

- SF-36 global and domain-specific scores at 6 and 12 months
- EQ-5D-5L summary index and visual analogue scale at six and twelve months
- AFEQT overall score at six and twelve months

Cardiac function:

- Echocardiographic LVEF at 12 months
- Diastolic function (E/e' and composite of diastolic indices) at 12 months
- Functional assessment
- Six-minute walking distance at 6 and 12 months
- Change in European Heart Rhythm Association (EHRA) class at 6 and 12 months

Biomarkers:

- Change in B-type natriuretic peptide (BNP) levels at 6 months
- Change in heart rate using 24-hour ambulatory ECG

12.1.3 Feasibility Outcomes

- Recruitment target of 3 patients per week across all participating centres.
- Compliance and reasons for non-compliance

- Number of withdrawals and losses to follow-up (with reasons)
- Drug discontinuation rate and adverse reactions requiring drug discontinuation.
- Number of patients needing therapy-induced requirement for additional treatment
- Population-specific standard deviations (SD) and proportions
 - *SD of SF36 physical functioning score at 6 and 12 months*
 - *SD of SF36 overall score at 6 and 12 months*
 - *SD of AFEQT overall score at 6 and 12 months*
 - *SD of LVEF and E/e' score at 6 and 12 months*
 - *Unplanned hospitalisation admissions rates*
- Cardiovascular Events (particularly mortality, thromboembolic events, myocardial infarction and cardiovascular interventions)

The final analyses will follow a pre-specified analysis plan, drafted in conjunction with the Birmingham Clinical Trials Unit and submitted to the steering committee at the penultimate meeting. We intend to perform a primary intention-to-treat analysis, in addition to a per-protocol analysis.

Any additional (exploratory) analyses will be explicitly labelled as such in any subsequent manuscript.

12.2 Power Calculations

Randomising 144 patients we can assume an 85% power to detect an effect size of half a standard deviation in a continuous outcome measure of QoL (two-sided alpha of 0.05). A sample size of 160 patients would account for an estimated 10% loss to follow-up (including withdrawal and death prior to 12-month assessment). There is some evidence from existing research to support the notion that the treatment effect could be this large. The mean SF-36 role-physical score from the rate-control arm of the RACE study was 47, with a 17% improvement with rate-control over time.⁶² In another study, CCB resulted in 22% improvement in a proprietary symptom-checklist, compared to a non-significant 8% change in those assigned to beta-blockers (SD 10-points in both groups). These values are also consistent with a 17% improvement in SF-36 scores in a third trial, PIAF.⁶³ Thus whilst it is possible that this trial may provide a clear indication of effect, it is accepted that the trial will be underpowered to detect smaller differences, reinforcing the requirement for a larger definitive trial which would also be powered to assess impact on clinical event rates.

12.3 Statistical analysis

A separate Statistical Analysis Plan for the RATE-AF trial provides a detailed description of the planned statistical analyses. A brief outline of these analyses is given below.

The primary comparison groups will be composed of those who are randomised to digoxin group and those randomised to the beta-blockers group. All analyses will be based on the intention to

treat principle, with all patients analysed in the arms to which they were allocated irrespective of compliance with the randomised allocated treatment, and all patients will be included in the analyses. We will, as a sensitivity analysis, conduct per-protocol analyses, where appropriate.

For all analyses, a p-value <0.05 will be considered statistically significant.

12.3.1 Primary outcome analysis

The primary outcome for this trial is the continuous SF36 physical functioning domain score at 6 months. This outcome will be analysed using an ANCOVA model adjusting for treatment arm, baseline score and all minimisation variables. Results will be presented as difference in means and 95% confidence intervals.

12.3.2 Feasibility and Secondary outcomes analysis

The feasibility and secondary outcomes for the trial comprise of a combination of both continuous and categorical (dichotomous) data items.

Categorical endpoints:

For outcomes which are categorical (dichotomous) in nature, the proportion of participants and percentages will be analysed between arms.

Logistic/Log-binomial regression models will be fitted (where appropriate) to adjust for treatment arm, baseline scores and all minimisation variables.

Results will be presented as odds ratios/relative risks and 95% confidence intervals.

Continuous endpoints:

Any outcomes that are continuous in nature will be analysed in the same way as the primary outcome.

12.3.3 Missing data and sensitivity analyses

Primary analysis will concentrate on available data only, with no attempt made to impute missing data. Where appropriate, sensitivity analyses will be carried out to examine the possible impact of missing data on the results (full details will be discussed within the Statistical Analysis Plan).

12.3.4 Interim analyses and Stopping rules

Analysis of the data with respect to efficacy and safety will be performed at 12 months and sent to Data Monitoring Committee (DMC); see **Section 16**. The DMC will outline and agree the stopping rules for the trial which will be documented in the DMC charter. It is likely that the Haybittle-Peto boundary will be used. This states that if an interim analysis shows a probability of less than 0.001 that the treatments are different, then the trial should be stopped early. This will be used alongside

data on important secondary endpoints and all other relevant evidence. A DMC report and charter outlining the terms of reference (including information on stopping rules) will be agreed with the DMEC.

12.4 Final analysis

The final analysis for the RATE-AF trial will occur once the last randomised participant completes their 12-month follow-up.

13 Ethics and Regulatory Requirements

The trial will be performed in accordance with the recommendations guiding physicians in biomedical research involving human participants, adopted by the 18th World Medical Association General Assembly, Helsinki, Finland, June 1964, amended at the 48th World Medical Association General Assembly, Somerset West, Republic of South Africa, October 1996 (website: <http://www.wma.net/en/30publications/10policies/b3/index.html>).

The trial will be conducted in accordance with the Research Governance Framework for Health and Social Care, the applicable UK Statutory Instruments, (which include the Medicines for Human Use Clinical Trials 2004 and subsequent amendments, the latest Data Protection legislation, the Human Tissue Act 2008, EU Clinical Trials Directive and amendment Regulations as appropriate) and Guidelines for Good Clinical Practice (GCP). This trial will be carried out under a Clinical Trial Authorisation in accordance with the Medicines for Human Use Clinical Trials regulations. The protocol will be submitted to and approved by the REC prior to circulation.

Before any participants are enrolled into the trial, the Principal Investigator at each site is required to obtain local R&D approval. Sites will not be permitted to enrol participants until written confirmation of R&D approval is received by the Principal Investigator.

It is the responsibility of the Principal Investigator to ensure that all subsequent amendments gain the necessary local approval. This does not affect the individual clinicians' responsibility to take immediate action if thought necessary to protect the health and interest of individual participants.

Within 90 days after the end of the trial, the Chief Investigator/Sponsor will ensure that the REC and the MHRA are notified that the trial has finished. If the trial is terminated prematurely, those reports will be made within 15 days after the end of the trial. The Chief Investigator will provide the Sponsor with a summary report of the clinical trial, which will then be submitted to the MHRA and REC within one year after the end of the trial.

14 Oversight Committees

14.1 Trial Management Group

The Trial Management Group (TMG) will comprise the CI, other lead investigators (clinical and non-clinical) and members of the BCTU. The TMG will be responsible for the day-to-day running and management of **RATE-AF**. The TMG will convene at regular intervals.

14.2 Trial Oversight Committee

A joint oversight committee comprising a Trial Steering Committee (TSC) and Data Monitoring Committee (DMC) will be engaged for this trial.

The role of the TSC is to provide the overall supervision of the trial. The TSC will monitor trial progress and conduct and advice on scientific credibility. The TSC will consider and act, as appropriate, upon the recommendations of the Data Monitoring Committee. Further details of the remit and role of the TSC are available in the TSC Charter.

An independent DMC will be established to oversee the safety of participants in the trial. The DMC will meet prior to the trial opening to enrolment, and then meet at least annually, or as per a timetable agreed by the DMC prior to trial commencement. Data analyses will be supplied in confidence to the DMC, which will be asked to give advice on whether the accumulated data from the trial, together with the results from other relevant research, justifies the continuing recruitment of further participants. The DMC will operate in accordance with the trial specific charter.

14.3 Protocol amendments

Where important protocol modifications are required as a result of oversight (for example, changes to eligibility criteria, outcomes or analyses), this information will be communicated to relevant parties, such as investigators, the REC, trial registries and regulators.

15 Finance

The **RATE-AF** Trial is funded through a Career Development Fellowship awarded to the Chief Investigator by the National Institute for Health Research (NIHR).

16 Confidentiality and Data Protection

Personal data recorded on all documents will be regarded as strictly confidential and will be handled and stored in accordance with the latest Data Protection legislation.

Participants will be identified using their unique trial identification number, date of birth and hospital number on the CRFs. and correspondence between the Trials Office and the participating site.

Participants will give their explicit consent for the movement of their consent form, giving permission for the Trials Office to be sent a copy. This will be used to perform in-house monitoring of the consent process.

The Investigator must maintain documents not for submission to the Trials Office (e.g. Participant Identification Logs) in strict confidence. In the case of specific issues and/or queries from the regulatory authorities, it will be necessary to have access to the complete trial records, provided that participant confidentiality is protected.

The Trials Office will maintain the confidentiality of all participants' data and will not disclose information by which participants may be identified to any third party other than those directly involved in the treatment of the participant and organisations for which the participant has given explicit consent for data transfer (e.g. competent authority, sponsor). Representatives of the **RATE-AF** Trials Office and sponsor may be required to have access to participant's notes for quality assurance purposes but participants should be reassured that their confidentiality will be respected at all times.

17 Insurance and Indemnity

The University of Birmingham has in place Clinical Trials indemnity coverage for this trial which provides cover to the University for harm which comes about through the University's, or its staff's, negligence in relation to the design or management of the trial and may alternatively, and at the University's discretion provide cover for non-negligent harm to participants.

With respect to the conduct of the trial at the Clinical Site and other clinical care of the patient, responsibility for the care of the patients remains with the NHS organisation responsible for the Clinical Site and is therefore indemnified through the NHS Litigation Authority.

The University of Birmingham is independent of any pharmaceutical company, and as such it is not covered by the Association of the British Pharmaceutical Industry (ABPI) guidelines for participant compensation.

18 Dissemination and Publication

Regular newsletters will keep collaborators informed of trial progress and regular meetings will be held to report the progress of the trial and to address any problems encountered in the conduct of the trial. The CI will coordinate dissemination of data from this trial. All publications and presentations, including abstracts, relating to the main trial will be authorised by the **RATE-AF** TMG. The results of the analysis will be published in the name of the **RATE-AF** Collaborative Group in a peer reviewed journal (provided that this does not conflict with the journal's policy).

Named authors must satisfy the International Committee of Medical Journal Editors (ICMJE) criteria for authorship (contribute to drafting of the article or revision for important intellectual content),

provide timely approval of the final version to be published and supply detailed statements on any potential conflict of interest or financial relationship (<http://www.icmje.org/>). Members of the group who do not fulfil ICMJE criteria for authorship will be listed in the article appendix. Trial participants will be sent a lay summary of the final results of the trial, which will contain a reference to the full paper.

19 References

APPENDIX B – Dosing Schedule (Bisoprolol)

This document is the Statistical Analysis Plan (SAP) for the RATE-AF trial, and should be read in conjunction with the current trial protocol. This SAP details the proposed analyses and presentation of the data for the main paper(s) reporting the results for the RATE-AF trial.

The results reported in these papers will follow the strategy set out here. Subsequent analyses of a more exploratory nature will not be bound by this strategy, though they are expected to follow the broad principles laid down here. The principles are not intended to curtail exploratory analysis (e.g. to decide cut-points for categorisation of continuous variables), nor to prohibit accepted practices (e.g. transformation of data prior to analysis), but they are intended to establish rules that will be followed, as closely as possible, when analysing and reporting data.

Any deviations from this SAP will be described and justified in the final report or publication of the trial (using a table as shown in Appendix A). The analysis will be carried out by an appropriately qualified statistician, who should ensure integrity of the data during their data cleaning processes.

2. Background and rationale

The background and rationale for the trial are outlined in detail in the protocol¹. In brief, Atrial fibrillation (AF) is an increasingly common cardiac condition that leads to a substantial burden on quality-of-life (QoL), an increased risk of cardiovascular events, hospitalisation and death, and significant healthcare costs for the NHS. Beta-blocker monotherapy remains the first-line option in the current NICE AF guidelines consultation document, with digoxin only for sedentary patients, although this recommendation is based on very low-quality evidence.

The Rate control Therapy Evaluation in Atrial Fibrillation (RATE-AF) trial is Prospective, Randomised Open-label Blinded Endpoint (PROBE) clinical trial comparing the use of digoxin and beta-blockers as initial rate control therapy. The RATE-AF trial combines hypothesis testing (quality of life, cardiac function, exercise capacity and biomarkers), evaluation of measures (validity, reproducibility and correlation of outcomes) and a feasibility study for a future clinical event trial (assessing recruitment, retention and sample size).

3. Trial objectives

The primary objective is the patient-reported QoL, with a predefined focus on physical well-being using the SF-36v2 physical component summary at 6 months.

Secondary objectives are as follows:

- Generic and AF-specific patient-reported QoL using the SF-36 global and domain-specific scores, the AFEQT overall score and the EQ-5D-5L summary index and visual analogue scale at 6 and 12 months.
- Echocardiographic left-ventricular ejection fraction (LVEF) and diastolic function (E/e' and composite of diastolic indices) at 12 months.
- Functional assessment, including 6-minute walking distance achieved, change in European Heart Rhythm Association (EHRA) class and cognitive function at 6 and 12 months.
- Change in B-type natriuretic peptide (BNP) levels as a surrogate for total cardiac strain at 6 months.
- Change in heart rate from baseline and group comparison using 24-hour ambulatory ECG.

Feasibility objectives:

- Successful methods for recruitment
- Key issues that affect retention of participants, such as convenience, compliance and cross-over (target

of 85% study completion rate).

- Drug discontinuation rate and adverse reactions leading to drug discontinuation.
- Therapy-induced requirement for additional treatment (e.g. pacemaker implantation).
- Population-specific standard deviations and proportions to enable sample size calculation for a future trial.
- Assessment of cardiovascular outcomes including a composite of adverse clinical events (mortality, thromboembolic events, myocardial infarction and cardiovascular interventions).

4. Trial methods

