3.3 Secondary objectives

- Generic and AF-specific patient-reported QoL using the SF-36 global and domain-specific scores, the AFEQT overall score and the EQ-5D-5L summary index and visual analogue scale at six and twelve months.
- Echocardiographic left-ventricular ejection fraction (LVEF) and diastolic function (E/e' and composite of diastolic indices) at twelve months.
- Functional assessment, including 6-minute walking distance achieved, change in European Heart Rhythm Association (EHRA) class and cognitive function at six and twelve months.
- Change in B-type natriuretic peptide (BNP) levels as a surrogate for total cardiac strain at six months.
- Change in heart rate from baseline and group comparison using 24-hour ambulatory ECG.

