3.5 Exploratory objectives

- Correlation of baseline measures, including QoL questionnaires and unblinded baseline investigations such as QoL, BNP, LVEF, E/e', EHRA, intracellular methods and heart rate.
- Impact of therapy on intracellular sodium and calcium concentration and cardiotonic steroid levels as biomarkers of cellular response at six and twelve months.
- Impact of combination therapy on outcomes, including comparison of bisoprolol/non-dihydropyridine calcium channel blocker (CCB) vs. bisoprolol/digoxin vs. digoxin/CCB vs. single therapies.
- Change in cognitive function at twelve months

- Qualitative research of patient-reported QoL using focus groups to explore patient acceptability, optimal delivery methods and responsiveness.
- Assessment of the validity and reproducibility of echocardiographic measures in patients with AF.
- Correlation of serum digoxin concentration with change in QoL and intracellular methods.
- Cost-consequence economic analysis from an NHS perspective.

4 Selection of Participants

Participants who potentially fulfil the inclusion criteria for this trial must have their eligibility confirmed by medically qualified personnel with access to and a full understanding of the potential participant's medical history. If eligibility has been assessed and documented by medically qualified personnel, then the process of obtaining informed consent may be delegated as appropriate and as documented on the **RATE-AF** Delegation and Signature Log.

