8.8 Trial Duration

Patients will be on trial medication for 12 months and will be followed-up, during this period according to the protocol. At the end of the 12 months, the participants may, as determined by their clinician, continue on medication but it will not be considered part of the trial intervention. The trial will cease when the 12-month follow-up has been completed for the last participant recruited.

Table 1: Schedule of Assessments

Procedures		Baseline Visit	Up-titration Visits (Day 14 to 60)	Visit 2, Month 6 (± 4 weeks)	Visit 3, Month 12 (± 4 weeks)
Assessment of eligibility criteria		X			
Informed consent taken		X			
Review of medical history		X			
Review of medications		X	X	X	X
Physical exam	Complete	X			
	Symptom-directed		X	X	X
	Vital signs	X	X	X	X
Quality of life assessment		X	(X)	X	X
Functional and cognitive assessment		X		X	X
Transthoracic echocardiogram		X			X
12-lead electrocardiogram		X		X	X
6-minute walk test		X		X	X
24-hour ambulatory ECG			X	(X)	
Clinical labs	Chemistry	X		X	X
	Haematology	X		X	X
	Serum digoxin			(X)	(X)
Trial labs	BNP	X		X	X
	Stored sample	X		X	
Assessment of compliance			X	X	X
Assessment of adverse events			X	X	X

Parentheses denote where a procedure is dependent on the stage of participants within the trial.

9 Trial Procedures

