4.4. Secondary outcome measures

Patient-reported QoL:

- SF-36 global and domain-specific scores at 6 and 12 months
- EQ-5D-5L summary index and visual analogue scale at 6 and 12 months
- AFEQT overall score at 6 and 12 months

Cardiac function:

- Echocardiographic LVEF at 12 months
- Diastolic function (E/e' and composite of diastolic indices) at 12 months
- Change in heart rate using 24-hour ambulatory ECG

Functional assessment:

- Six-minute walking distance at 6 and 12 months
- Change in European Heart Rhythm Association (EHRA) class at 6 and 12 months

Biomarkers:

- Change in B-type natriuretic peptide (BNP) levels at 6 and 12 months

Feasibility outcomes:

- Recruitment target of 3 patients per week across all participating centres
- Compliance and reasons for non-compliance
- Number of withdrawals and losses to follow-up (with reasons)
- Drug discontinuation rate and adverse reactions requiring drug discontinuation

- Number of patients needing therapy-induced requirement for additional treatment
- Cardiovascular events (mortality, thromboembolic events, myocardial infarction and cardiovascular intervention)
- Population-specific standard deviations (SD) and proportions for all outcomes

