9.7. Analysis methods – exploratory outcomes and analyses

Any data that does not form a pre-specified outcome will be presented using simple summary statistics by intervention group (i.e. numbers and percentages for binary data and means (or medians) and standard deviations (or inter-quartile ranges) for continuous normal (or non-normal) data.

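### Cognitive function is a secondary objective at 6 and 12 months, but it is in no outcome list and has no pre-specified between-arm estimate; the protocol also lists it as exploratory at 12 months only

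*SAP*

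**What the plan says.** Protocol 3.3 and SAP section 3 set the same secondary objective for functional assessment. It has three components: six-minute walking distance, EHRA class and cognition. The protocol's wording ends "class and cognitive function at six and twelve months"; the SAP's is "change in European Heart Rhythm Association (EHRA) class and cognitive function at 6 and 12 months".

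Protocol 3.5, the exploratory objectives, has a separate line: "Change in cognitive function at twelve months".

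The schedules (protocol Table 1, SAP Appendix C) have a row "Functional and cognitive assessment", marked at baseline, month 6 and month 12.

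The functional part of the outcome lists contains two items only. One is "Six-minute walking distance at 6 and 12 months" (protocol 12.1.2). The other is "Change in European Heart Rhythm Association (EHRA) class at 6 and 12 months" (SAP 4.4). The protocol summary has the same pair.

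For anything outside the listed outcomes, SAP 9.7 states: "Any data that does not form a pre-specified outcome will be presented using simple summary statistics by intervention group".

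**The concern.** A secondary objective in a randomised trial is a commitment to compare the arms on that measure. Here the commitment is made in both documents and an assessment is scheduled at three visits, but nothing between the objective and the final tables turns it into an estimate of effect. If the SAP is followed exactly, the main report can show cognitive data by arm but has no planned difference, confidence interval or baseline adjustment to put beside them.

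The second problem is the double listing. The same measure is secondary at two time points and exploratory at one. With no rule saying which applies, its standing in the report, and whether month 6 counts, is not settled in advance.

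**Working it through.** No arithmetic carries this point. The check is to follow the three components of the one objective through both documents.

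| Place | Six-minute walk | EHRA class | Cognitive function |
|---|---|---|---|
| Secondary objectives (protocol 3.3, SAP 3) | yes | yes | yes, 6 and 12 months |
| Exploratory objectives (protocol 3.5) | no | only in baseline correlations | yes, 12 months only |
| Outcome lists (protocol summary, protocol 12.1.2, SAP 4.4) | yes | yes | absent from all three |
| Derivation (SAP 9.4) | not needed, distance is recorded directly | yes | none |
| Model (SAP 9.6) | linear regression as in 9.5 | ordinal and binary logistic | none |
| Results template (SAP D6) | yes | yes | none |

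Four things follow.

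1. The walk test and EHRA class each run from objective to outcome to model to table. Cognition stops at the objective and the schedule. That pattern looks like an oversight, although the documents do not say so.

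2. Because cognition is on no outcome list, the rule that most naturally governs it is SAP 9.7. That rule provides counts and percentages, or means (or medians) with a measure of spread, by arm. It provides no effect estimate and no confidence interval.

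3. The protocol's two objectives lists disagree on status (secondary against exploratory) and on timing (6 and 12 months against 12 months).

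4. Neither document names a cognitive instrument, a score or a scale type. The visit procedures in protocol 8.1, 8.3 and 8.4 mention quality-of-life and functional capacity questionnaires but no cognitive test, and protocol section 9 describes none. The only evidence of collection is the combined schedule row. Adding cognition to an outcome list would therefore not by itself make it analysable.

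The size of the gap is one of three components of one secondary objective, at two time points: 1 × 2 = 2 between-arm comparisons without a pre-specified method.

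**The case against.** Four arguments run the other way.

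**General wording may cover it.** Protocol 12.3.2 analyses continuous outcomes like the primary outcome, and SAP 9.1 adjusts all outcomes for baseline score where appropriate. This is arguable, but both provisions speak of outcomes and cognition is not listed as one. With no score defined, it is also unknown whether it is continuous. The general wording does not clearly reach it.

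**The status may already be settled as exploratory.** Protocol section 3 refers the reader to section 12 for the detailed outcome measures. All three outcome lists omit cognition and protocol 3.5 calls it exploratory. This is a fair reading, and it is why the fix must leave the choice of status to the sponsor. It does not remove the defect, because on that reading protocol 3.3 and SAP 3 are wrong and need correcting.

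**There are safeguards against selective reporting.** Protocol 12.1.3 requires additional exploratory analyses to be labelled as such, and SAP section 1 requires deviations to be described and justified. A reader might infer from the double listing that the team is free to choose the prominence of the result after seeing it. These rules limit that freedom, so the inference goes too far. What stands is that the label itself is undecided.

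**More tests in an uncorrected plan.** SAP 5.2 makes no multiplicity adjustment, so each added comparison has a cost. That is true, but the addition is small. The quality-of-life part of SAP 9.6 alone already has 25 secondary comparisons: physical summary at 12 months (1), mental summary and eight domains at two times (9 × 2 = 18), EQ-5D index and visual scale at two times (2 × 2 = 4), and AFEQT at two times (2).

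**Conclusion.** The point holds as an inconsistency between objectives and outcomes, with a practical consequence: a declared secondary objective has no pre-specified between-arm estimate or confidence interval at 6 or 12 months, and its status and time points conflict within the protocol.

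A reader might go further and infer that cognition will not be analysed at all, or that the randomised comparison cannot be made. The documents do not support that. SAP 9.7 would still present the data by randomised arm, and SAP section 1 leaves later exploratory analyses open. What is missing is a planned, formal comparison in the main analysis.

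The conclusion rests on two readings: that SAP 9.7 governs a measure on no outcome list, and that the schedule row means a cognitive test is actually given at the three visits. The primary outcome and the sample size do not depend on any of this. It should be corrected, but it does not threaten the trial's main result.

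**What to change.** First decide the status and time points, and name the cognitive instrument, its score and its scale type. Then follow one of two routes.

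- **If secondary:** define the score in SAP 9.4. Add it at 6 and 12 months to protocol 12.1.2 (and the protocol summary), SAP 4.4, SAP 9.6 and Appendix D6. If the score is continuous, use the SAP 9.5 model with baseline cognitive score, minimisation variables, age and baseline LVEF. Otherwise use the matching logistic or ordinal model, as the SAP already does for the diastolic composite and EHRA class. Delete the line in protocol 3.5.
- **If exploratory:** remove cognition from protocol 3.3 and SAP 3 and state its time points. Under SAP 9.7, specify the same baseline-adjusted estimate with a 95% confidence interval, labelled exploratory.

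Either route needs a little protocol and SAP wording and a few model runs, with no change to the scheduled visits. The downside is up to two more comparisons in a plan with no multiplicity correction, which is a reason to emphasise the estimate and its interval over the p-value.
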